- mPFS-1: Historically, the mPFS for previously treated mCRC patients treated with RGF is 1.9 mos. We predict VOR/HCQ will improve mPFS to 3.8 months. We expect 5% lost to follow-up. Assuming a 36-month accrual period with 1 year for follow up, 36 subjects per group are necessary to obtain 80% power. With 5% lost to follow-up the sample size required per group is 38 ($=36/0.95$), therefore, the total required sample size is 76 subjects. As a result, the target accrual rate is 2-4 patients/month to achieve a target accrual at 36 months with an additional 12-month follow-up.

Interim analysis: The O'Brien-Fleming procedure will be used to conduct an interim analyses for efficacy when 50% of the patients complete the study. A statistical basis for stopping the study at the first look will be achieved if the test statistic indicates benefit in the VOR/HCQ Arm and exceeds 2.96259, corresponding to a significance level of 0.003. If the test statistic does not exceed 2.96259 at the first look then the trial will proceed to the final analysis. A treatment effect will be declared significant and beneficial at the final analysis if the test statistic indicates benefit and exceeds 1.96857, corresponding to a significance level of 0.047. If a treatment effect is not declared at the interim analysis, a statistical basis for stopping the study for futility will be attained if the conditional power is less than or equal to 20%.

Analytic plan for secondary objectives:

- OS: The analyses of median OS will be performed in the intent-to-treat population. OS will be illustrated with Kaplan-Meier plots, the estimate of median OS with its 95% confidence interval.
- mPFS-2: The analyses of median PFS-2 will be performed in the crossover population (crossover is optional). mPFS-2 will be illustrated with Kaplan-Meier plots, the estimate of median PFS-2 with its 95% confidence interval. Treatment groups will be contrasted with regard to the response rate with a logistic regression model adjusted for age, sex, race and the baseline tumor K-RAS status (mutated, wild type); the odds ratio, its 95% confidence interval, and the p-value for testing the null hypothesis that the log odds ratio is zero will be presented. If the logistic model fails due to small cell counts then treatments will be contrasted with regard to response using Fisher's Exact Test.

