3.0 Statement of Study Objectives

Primary Objective:

- To determine the clinical efficacy with progression-free survival (PFS-1) of the combination of VOR plus HCQ when compared to RGF in treatment-refractory mCRC.

Secondary Objectives:

- To determine the overall survival in refractory mCRC patients receiving VOR plus HCQ when compared to RGF.
- To determine the progression-free survival (PFS-2) of the crossover treatment (crossover is optional).
- To evaluate the tumor response rate in refractory mCRC patients receiving VOR plus HCQ when compared to RGF.
- To further define the safety of the combination of VOR/HCQ when compared to RGF in treatment-refractory mCRC.
- To identify biomarkers of autophagy and anti-angiogenic inhibition that are associated with clinical efficacy of VOR/HCQ and RGF, respectively, in mCRC.

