5.3 Treatment Requirements

All eligible patients who consent to this study must have a baseline evaluation (CT or MRI) within 6 weeks of the start of treatment.

Patient must meet all eligibility requirements to be entered onto the protocol.

5.3.1 Duration of Intervention and Evaluation:

Follow-up: A repeat CT scan will be performed after 2 cycles of treatment regimen to evaluate response based on RECIST 1.1 criteria (See Appendix 13.1 for definitions of response) (73). CT scans will be repeated at least every 2 cycles, or 8 weeks, to ensure no progression of disease. Patients will continue on VOR/HCQ or RGF until disease progression, unacceptable toxicity, withdrawal of consent by the patient, or decision of physician for patient's best interest. Crossover to the other arm will be allowed, but OPTIONAL, and will be determined by the treating physician for the patient's best interest. If patient is not given crossover treatment, then the patient will be off study and will be allowed to receive subsequent treatments. Each patient

will be followed for 1 year. We will follow the last patient for 12 months, at which time, the study will be completed for data analysis.

Interim analysis: The O'Brien-Fleming procedure will be used to conduct an interim analyses for efficacy when 50% of the patients complete the study. A statistical basis for stopping the study at the first look will be achieved if the test statistic indicates benefit in the VOR/HCQ Arm and exceeds 2.96259, corresponding to a significance level of 0.003. If the test statistic does not exceed 2.96259 at the first look then the trial will proceed to the final analysis. A treatment effect will be declared significant and beneficial at the final analysis if the test statistic indicates benefit and exceeds 1.96857, corresponding to a significance level of 0.047.

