- OS: The analyses of median OS will be performed in the intent-to-treat population. OS will be illustrated with Kaplan-Meier plots, the estimate of median OS with its 95% confidence interval. Treatment groups will be contrasted with regard to the response rate with a logistic regression model adjusted for age, sex, race and the baseline tumor K-RAS status (mutated, wild type); the odds ratio, its 95% confidence interval, and the p-value for testing the null hypothesis that the log odds ratio is zero will be presented. If the logistic model fails due to small cell counts then treatments will be contrasted with regard to response using Fisher's Exact Test.
- mPFS-2: The analyses of median PFS-2 will be performed in the crossover population. Crossover to the other arm will be allowed, but OPTIONAL, and will be determined by the treating physician for the patient's best interest. mPFS-2 will be illustrated with KaplanMeier plots, the estimate of median PFS-2 with its 95% confidence interval. Treatment groups will be contrasted with regard to the response rate with a logistic regression model adjusted for age, sex, race and the baseline tumor K-RAS status (mutated, wild type); the odds ratio, its 95% confidence interval, and the p-value for testing the null hypothesis that the log odds ratio is zero will be presented. If the logistic model fails due to small cell counts then treatments will be contrasted with regard to response using Fisher's Exact Test.
- Response rates: Response rates will be measured as the proportion of patients with the best response, complete response (CR) or partial response (PR), as defined by RECIST 1.1 Criteria and a 95% confidence interval. (See Appendix 13.2 for RECIST 1.1 criteria)
- Adverse events: All adverse events will be listed by type and grade. All adverse events will be listed by treatment group, level of seriousness (serious, not serious). Treatments will be contrasted with regard to each adverse event with Fisher's Exact Test.

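### The mPFS-2 bullets order a between-group test of response rate right after naming the physician-selected crossover population and give it no other population, so read as written it is a non-randomised comparison

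*Combined protocol and SAP*

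**What the plan says.** **The mPFS-2 bullet, Section 10.0.** It sets the population first: "The analyses of median PFS-2 will be performed in the crossover population". It then says how patients enter that population: "Crossover to the other arm will be allowed, but OPTIONAL, and will be determined by the treating physician for the patient's best interest". PFS-2 itself is to be summarised by a Kaplan-Meier plot and "the estimate of median PFS-2 with its 95% confidence interval". The next sentence turns to another endpoint: "Treatment groups will be contrasted with regard to the response rate with a logistic regression model adjusted for age, sex, race", and baseline K-RAS. For that model "the p-value for testing the null hypothesis that the log odds ratio is zero will be presented", with the odds ratio and its 95% CI; Fisher's Exact Test is the fallback for small cells.

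**The synopsis (Section 1.0, Analytic plan for secondary objectives).** The mPFS-2 bullet has the same structure. It is the only place in the synopsis where a between-arm response contrast appears.

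**Neighbouring bullets.** In Section 10.0 the OS bullet carries the same logistic/Fisher text, and its stated population is intent-to-treat. The Response rates bullets, in both the synopsis and Section 10.0, give a proportion with a 95% CI and no contrast.

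**Objectives, Section 3.0.** The PFS-2 objective, "To determine the progression-free survival (PFS-2) of the crossover treatment (crossover is optional"), names no comparator. The OS and response objectives both compare VOR/HCQ with RGF.

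**Patients who do not cross over, Section 5.3.1.** "If patient is not given crossover treatment, then the patient will be off study and will be allowed to receive subsequent treatments".

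**The concern.** A crossover patient has come through the first drug, remained fit enough for a second, and been chosen for it by a treating physician who knows the first drug. None of this is protected by the 1:1 randomisation. The adjustment set contains nothing measured at crossover: no ECOG at that time, no length of PFS-1, no reason for leaving the first drug.

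The documents give reasons why selection could differ between arms:

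- Under the trial's own hypothesis (median PFS-1 of 3.8 v 1.9 months) the arms reach crossover at different times and after different benefit.
- The synopsis describes RGF as standard therapy, so a VOR/HCQ-arm patient who leaves the study may be able to receive it elsewhere.
- The trigger for crossover is stated in two ways. Synopsis, Study Design, says after first progression; Synopsis, Intervention and Mode of Delivery, says progression or unacceptable toxicity. Under the second, an arm with more intolerable toxicity would send more patients into PFS-2 before they have progressed.

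The plan also leaves *treatment groups* undefined once patients have switched. It could mean the randomised arm or the drug now being taken, and the odds ratio inverts between the two.

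At stake is a reported odds ratio and p-value for response that a reader would take as evidence about the drugs. Meanwhile the comparative response objective has no contrast under its own endpoint.

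**Working it through.** **1. The plan's own figures.** No sample size, power or expected crossover count is given for PFS-2. The only sample size is for PFS-1, and it reproduces assuming a two-sided 0.05 level. Freedman events at HR 1.9/3.8 = 0.5: (1.960 + 0.842)² × (1.5/0.5)² = 70.6, so 71. Mean event probability with exponential survival, 36 months' accrual and 12 months' follow-up is 0.991; 71/0.991/2 = 35.8, so 36 per group; 36/0.95 = 37.9, so 38 per group and 76 in total. Nothing below changes these.

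**2. Selection with continuous fitness.** All inputs except the 1.9-month median and the 38 per arm are assumptions, since the documents give no crossover or second-line response rates:

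- Frailty F ~ N(0,1); higher F is worse.
- Response: logit slope -0.8 per unit F, 8% overall.
- Crossover: logit slope -1 or -2 per unit F, with the intercept set to each arm's crossover rate.
- The second drugs are equally effective, and no adjustment covariate is related to F.

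Response among crossovers is E[P(response|F) × P(cross|F)] / E[P(cross|F)]. The arm that crosses fewer patients is more selected, so it shows the higher rate.

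| Crossover rates | Slope | Response, higher-rate arm | Response, lower-rate arm | Odds ratio (lower v higher) |
|---|---|---|---|---|
| 50% v 50% | -1 / -2 | equal | equal | 1.00 |
| 60% v 40% | -1 | 9.75% | 10.87% | 1.13 |
| 60% v 40% | -2 | 10.49% | 12.24% | 1.19 |
| 70% v 30% | -1 | 9.27% | 11.57% | 1.28 |
| 70% v 30% | -2 | 9.79% | 13.41% | 1.43 |
| 80% v 30% | -1 | 8.83% | 11.57% | 1.35 |
| 80% v 30% | -2 | 9.16% | 13.41% | 1.54 |

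Example: (0.1341/0.8659) / (0.0979/0.9021) = 0.1549/0.1085 = 1.43.

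**3. A second model as a check.** Half of each arm has good prognosis. Response among crossovers is (c_g r_g + c_p r_p)/(c_g + c_p), where c is the crossover probability and r the response rate in good (g) and poor (p) prognosis patients. Suppose one arm crosses 70% of good and 30% of poor, the other 50% of each, with r_g = 10% and r_p = 2%. Then 0.7 × 0.10 + 0.3 × 0.02 = 7.6% against 6.0%, and the odds ratio is (0.076/0.924)/(0.060/0.940) = 1.29. Across response pairs 5%/0%, 10%/2% and 30%/5%, with the selecting arm at 70/30 or 80/20, the range is 1.3 to 1.6. Only fully opposite selection (80/20 v 20/80) gives 2.5 to 4.1. Identical selection gives 1.0.

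**4. How often would Fisher's test be falsely significant?** Exact enumeration for step 2's unequal scenarios with 38 per arm (23 v 15, 27 v 11 and 30 v 11 crossovers): p ≤ 0.05 in 1.3% to 3.5% of trials, below the nominal 5%. In step 3 the rate is about 0.1% to 5% under moderate selection and reaches 15% only under opposite selection with the highest response rates.

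**5. Could the test find a real difference?** With true response of 5% v 15%, Fisher's test reaches p ≤ 0.05 in about 1% (11 v 23 crossovers), 6% (19 v 19) or 10% (23 v 11) of trials.

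**6. Direction.** Suppose the RGF arm crosses 70% and the VOR/HCQ arm 30%. Labelled by randomised arm, the spurious 1.43 reads as favouring VOR/HCQ, although those patients are now taking RGF. Labelled by current drug, VOR/HCQ v RGF is 1/1.43 = 0.70.

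**The case against.** The strongest reply is that this is a drafting slip. The sentence on the crossover population governs the analyses of median PFS-2, and nothing explicitly says that the response contrast uses it. The identical text under OS, where the population is intent-to-treat, and the gap under Response rates both suggest text displaced from the Response bullet. That is plausible, and it means the documents do not show an intention to test in crossover patients. It does not remove the problem: the bullet offers no other population, so an analyst following it literally would run the contrast in crossover patients.

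A reader might infer stronger things that the documents do not support:

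- *That PFS-2 is compared between groups.* It is not. No log-rank test or hazard model is specified for it; the odds ratio and p-value concern response.
- *That the group label is reversed.* It is undefined, which is an ambiguity. Reversal follows only if the contrast is run in crossover patients and labelled by randomised arm.
- *That false-positive claims are likely.* At this sample size they are mostly rarer than 5%.
- *That RGF-arm patients can obtain VOR/HCQ only by crossing over, or that selection will differ by a known amount.* The first is an inference; for the second the documents give no figure.

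It is also fair to say that the endpoint is secondary. Simply deleting the contrast would do harm, because the synopsis would then have no between-arm response analysis for a comparative objective.

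**Conclusion.** The concern holds in a limited form. As written, the mPFS-2 bullets attach a response-rate odds ratio, CI and p-value to a physician-selected population formed after randomisation, with covariates that do not describe patients at crossover. Under the assumptions shown, two equal second drugs would give an odds ratio of about 1.1 to 1.5 through selection alone, and 1.0 if both arms select alike. Those sizes rest on assumed crossover rates, response rates and strength of selection; the documents fix none of them. The damage is a biased and directionally ambiguous estimate from a test with little power, together with a comparative response objective that has no contrast under its own heading. PFS-1, the sample size and the descriptive PFS-2 summary are unaffected. The change is worth making because it costs only wording.

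**What to change.** 1. Remove the logistic/Fisher response contrast from the mPFS-2 bullets (synopsis and Section 10.0) and from the OS bullet in Section 10.0.
2. Place it once under Response rates, in both the synopsis and Section 10.0, for response on the first randomised treatment, by randomised arm, in the intent-to-treat population. Tying it to the first treatment matters because Section 7.0 records best response at any time.
3. Report PFS-2 (Kaplan-Meier median, 95% CI) and response on the second drug descriptively for each sequence: RGF then VOR/HCQ, and VOR/HCQ then RGF. Label each by the drug being received.
4. Beside these, show per arm the number eligible for crossover and the number who crossed over, the reason for crossover, ECOG at crossover and PFS-1 length.
5. State that the two sequences are not a randomised comparison and that no between-sequence p-value will be given.
6. Reconcile the two statements of the crossover trigger in the synopsis (Study Design; Intervention and Mode of Delivery), because together they define who is eligible and hence the PFS-2 population.

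Cost: one non-randomised p-value is given up. ECOG is already scheduled at each cycle and at progression (Section 6.0), and PFS-1 is already recorded (Section 7.0); the reason for crossover must be captured if the case report form does not already do so. The 76 patients and the primary analysis stay as they are.

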- if the event was part of the normal disease process, and
- what actions were taken as a result of the event.

Safety Definitions:

For this study, the following safety definitions will be applicable:

Adverse Event Definition: An adverse event (AE) is defined as any untoward or unfavorable medical occurrence in a human subject, including any abnormal sign (for example, abnormal physical exam or laboratory finding), symptom, or disease, temporally associated with the subject's participation in the research, whether or not considered related to the subject's participation in the research. For this study, all adverse events will be documented starting with the first dose of the study drug and ending 30 days after the last dose of study drug is received.

Serious Adverse Event Definition: is any adverse event that:

1. results in death;
2. is life-threatening (places the subject at immediate risk of death from the event as it occurred);
3. results in inpatient hospitalization or prolongation of existing hospitalization;
4. results in a persistent or significant disability/incapacity;
5. results in a congenital anomaly/birth defect; or
6. based upon appropriate medical judgment, may jeopardize the subject's health and may require medical or surgical intervention to prevent one of the other outcomes listed in this definition

Unanticipated Problems Involving Risks to Subjects or Others Definition: Unanticipated problem involving risk to subjects or others includes any incident, experience or outcome that meets all of the following criteria:

- A. unexpected (in terms of nature, severity, or frequency) given (a) the research procedures that are described in the protocol-related documents, such as the IRB-approved research protocol and informed consent document; and (b) the characteristics of the subject population being studied (note: the unfounded classification of a serious adverse event as "anticipated" constitutes serious non-compliance);
- B. definitely related or probably related to participation in the research; and
- C. suggests that the research places subjects or others at a greater risk of harm (including physical, psychological, economic, or social harm) than was previously known or recognized

Reporting Requirements

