10.0 Statistical Section

Analytic plan for primary objective:

mPFS-1: Historically, the mPFS for previously treated mCRC patients treated with RGF is 1.9 mos. We predict VOR/HCQ will improve mPFS to 3.8 months. We expect 5% lost to followup. Assuming a 36-month accrual period with 1 year for follow up, 36 subjects per group are necessary to obtain 80% power. With 5% lost to follow-up the sample size required per group is 38 ($=36/0.95$), therefore, the total required sample size is 76 subjects. As a result, the target accrual rate is 3-4 patients/month to achieve a target accrual at 36 months with an additional 12month follow-up.

Treatments will be contrasted with regard to PFS-1 with a proportional hazards model with adjustment for age, sex, race, and the baseline tumor K-RAS status (mutated, wild type); the adjusted hazard ratio, its 95% confidence interval, and the p-value for testing the null hypothesis that the log hazard ratio is zero will be presented. Survival curves will be illustrated with Kaplan-Meier plots. Interactions between treatment and baseline covariates will be explored.

If a patient does not complete Cycle 1 and is off study, then this patient will not be evaluable for efficacy but will be evaluable for toxicity.

Interim analysis: The O'Brien-Fleming procedure will be used to conduct an interim analyses for efficacy when 50% of the patients complete the study. A statistical basis for stopping the study at the first look will be achieved if the test statistic indicates benefit in the VOR/HCQ Arm and exceeds 2.96259, corresponding to a significance level of 0.003. If the test statistic does not exceed 2.96259 at the first look then the trial will proceed to the final analysis. A treatment effect will be declared significant and beneficial at the final analysis if the test statistic indicates benefit and exceeds 1.96857, corresponding to a significance level of 0.047. If a treatment effect is not declared at the interim analysis, a statistical basis for stopping the study for futility will be attained if the conditional power is less than or equal to 20%.

Analytic plan for secondary objectives:

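### The only between-arm adverse event test ignores time at risk, which the plan expects to be longer on VOR/HCQ, so events that accrue over time are compared with a tilt against VOR/HCQ

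*Combined protocol and SAP*

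**What the plan says.** A secondary objective in Section 3.0 is comparative: "To further define the safety of the combination of VOR/HCQ when compared to RGF in treatment-refractory mCRC". The synopsis only lists adverse events by type and grade. Section 10.0 adds listings by treatment group and seriousness, and one test: "Treatments will be contrasted with regard to each adverse event with Fisher's Exact Test". No level is stated for these tests. Neither place gives person-time rates, time to first event or a fixed comparison window.

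Three other statements set how long each patient is observed for adverse events:
- Section 5.3.1: "Patients will continue on VOR/HCQ or RGF until disease progression, unacceptable toxicity, withdrawal of consent by the patient, or decision of physician" in the patient's best interest.
- Section 8.0, Safety Definitions: events are "documented starting with the first dose of the study drug and ending 30 days after the last dose of study drug".
- Section 10.0: "Historically, the mPFS for previously treated mCRC patients treated with RGF is 1.9 mos", followed by "We predict VOR/HCQ will improve mPFS to 3.8 months".

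Section 5.4.2.2 has the number of VOR days and the total VOR dose recorded on the case report form, but no analysis uses them.

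**The concern.** A Fisher's test on each event needs a yes or no per patient. A patient watched for longer has more opportunity to become a yes. Here the length of observation depends on efficacy: the better VOR/HCQ delays progression, the longer its patients are treated and the longer their events are collected. The two arms have equal windows only if the efficacy hypothesis fails.

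Two errors would follow for events that accrue over time. Equal monthly rates would tend to look like more toxicity on VOR/HCQ, and a lower monthly rate on VOR/HCQ would be partly or wholly hidden. The issue is separate from crossover, because it remains if each patient is counted only on the randomised drug.

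**Working it through.** **1. The plan's own figure.** The documents give no figure for the adverse event comparison, so the check starts from the sample size, which uses the same medians. With exponential PFS the hazard ratio is 1.9/3.8 = 0.5. Freedman's formula at two-sided 0.05 and 80% power gives (1.960 + 0.842)² × (1.5/0.5)² = 7.85 × 9 = 70.6, so 71 events. The mean event probability with 36 months of accrual and 12 of follow-up is 0.991, and 71/0.991 = 71.6 patients, or 36 per group. Then 36/0.95 = 37.9, or 38. The plan's figures are reproduced, and 38 per arm and two-sided 0.05 are used below. The 0.05 for adverse event tests is an assumption.

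**2. Observation window.** The documents state no treatment duration. Assume that time on treatment is exponential with the PFS medians, so μ = ln 2/median = 0.365 and 0.182 per month (means 2.74 and 5.48 months). Add 1 month for the 30-day tail and cap at 12 months. The mean window is 1 + (1/μ)(1 − e^(−11μ)):
- RGF: 1 + 2.74 × 0.982 = 3.69 months
- VOR/HCQ: 1 + 5.48 × 0.866 = 5.74 months

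The ratio is 1.56. If treatment instead stops only at the 8-weekly scans (Sections 5.3.1 and 6.2), each time is rounded up to a multiple of 56/30.4 = 1.84 months. The means become 4.70 and 6.58 months, ratio 1.40.

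**3. Event proportions.** With constant hazard λ, the probability of at least one event is 1 − E[e^(−λW)], where W is the window. Before the cap this is 1 − e^(−λ) μ/(λ+μ). For RGF at λ = 0.2 it gives 1 − 0.819 × 0.365/0.565 = 47%.

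**4. Test behaviour.** Fisher's test was enumerated over all 39 × 39 tables; the log-rank test on time to first event was simulated.

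| Scenario (RGF v VOR/HCQ hazard per month) | Exposure model | Proportions | Fisher | Log-rank |
|---|---|---|---|---|
| Equal, 0.1 | continuous | 29% v 40% | 13% | 5% |
| Equal, 0.2 | continuous | 47% v 60% | 15% | 6% |
| Equal, 0.1 | 8-week scans | 36% v 45% | 9% | 5% |
| Equal, 0.2 | 8-week scans | 57% v 67% | 10% | 6% |
| Halved, 0.2 v 0.1 | continuous | 47% v 40% | 6% | 48% |
| Halved, 0.2 v 0.1 | 8-week scans | 57% v 45% | 12% | 55% |

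In the equal-hazard rows almost all Fisher rejections go against VOR/HCQ. If half the patients stop between scans, Fisher gives 10–12% at equal hazards and about 9% for the halved hazard.

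**5. Baselines.** With equal proportions of this size Fisher's true rejection rate at 38 per arm is about 3%. With both arms observed for the RGF duration under continuous exposure, it finds the halved hazard in 29% of trials (47% v 29%), or 23% if the 30-day tail is left out. Under scan timing the matching figure is 37% (57% v 36%).

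**6. Early events.** If the hazard acts only in the first two cycles and the RGF proportion is 47%, Fisher's rejection rate at equal hazard is about 3% with the 30-day tail (5.5% without it). A halved hazard is then found in 31–34% of trials.

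**7. Large differences.** Section 2.2.1 quotes, for RGF against placebo, hand-foot syndrome 47% v 8%, hypertension 28% v 6% and grade 3 or higher events 54% v 14%. If VOR/HCQ showed the placebo proportions over its whole, longer window (an assumption), Fisher's power at 38 per arm is 97%, 67% and 95%.

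**The case against.** The strongest reply is that the size of the effect rests on assumptions the documents do not supply. They give PFS, not time on treatment, and no onset data. Safety monitoring is concentrated early, with liver tests every two weeks in the first 2 months on RGF and Day 15 bloods only in Cycles 1 and 2. If most toxicity arises then, Fisher's test is adequate. This stands, and it is why the point is limited to events that accrue over time. Such events are not hypothetical: Section 2.3.2 describes chloroquine retinopathy as cumulative, and the plan tests every event, not only early ones.

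A second reply is that whole-period incidence on a drug given to progression legitimately describes cumulative burden, and that these are secondary tests in a 76-patient phase II trial with separate toxicity stopping rules. This also stands as a reason to keep the incidence table. It does not justify a p-value from that table as the only between-arm comparison.

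Two stronger readings are tempting. A reader might infer that exposure doubles because median PFS doubles. The documents do not say so, and with the 30-day tail, the cap and realistic scan timing the mean window ratio is 1.4 to 1.6. A reader might also infer that better tolerability could not be shown. Step 7 contradicts that for differences as large as those between RGF and placebo. Nor is the whole gap between 6–12% and 48–55% due to unequal exposure: Fisher's power is modest at this sample size even with equal windows.

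**Conclusion.** The point holds, within limits. The planned test takes no account of time at risk, the plan's own efficacy prediction makes that time longer on VOR/HCQ, and nothing in the documents corrects for it. For accruing events, equal hazards are declared different in about 9–15% of trials, against about 3% for the same test with equal windows and about 5% for log-rank. A halved hazard is shown in 6–12% of trials by Fisher's test and 48–55% by log-rank.

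These figures assume a constant hazard of 0.1–0.2 per month, exponential PFS at the planned medians and 38 per arm. With a PFS ratio of 1.5 instead of 2 the distortion shrinks (47% v 55%, Fisher 6.8%). It vanishes if exposure is equal and reverses if RGF patients stay on longer. Events confined to the first two cycles are essentially unaffected. Better tolerability is therefore harder to show for accruing events, but not impossible. The primary analysis is untouched. Severity is moderate: a cheap improvement to a secondary objective.

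**What to change.** Amend the adverse event paragraph of Section 10.0 so that:
- the between-arm comparison of each event is time to first occurrence on the randomised drug only, with a cause-specific hazard ratio and log-rank test;
- patients are censored 30 days after the last dose of that drug, or at the start of crossover treatment if earlier, with progression and death named as competing events and their handling stated;
- events per patient-month are reported by arm;
- Fisher's test is kept for a fixed window, Cycles 1–2;
- the whole-period incidence table by arm and grade stays, labelled as description of cumulative burden.

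The cost is new wording, one more table, and onset and last-dose dates for both arms in the analysis file. VOR days are already recorded; the documents do not state the same for RGF. One limitation remains and should be acknowledged: stopping for progression or toxicity may be informative censoring, so the hazard comparison should be read beside the incidence table. Treatment and sample size do not change.
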